### 2.2 Participants

Participants for this study will be recruited through health-related entry pathways, such as health clinics, gender-focused support services, community hubs, and ministries and stakeholders working within the mental health sector in Afghanistan. Participants will be men and women between the ages of 16 and 30 residing in Afghanistan, who experience psychological distress. Eligible participants will have elevated levels of psychological distress measured by the Kessler-10 Psychological Distress Scale (K10 > 15) (Andrews, 2001). They should also meet the inclusion criteria of having the ability to read and write in Dari. Those who present as an imminent suicide risk, with psychosis, or those with neurological or cognitive disabilities, will be excluded. Potential participants will be asked to provide their contact information and will be invited to complete the K10 self-report assessment, to measure their level of psychological distress. Once determined as having elevated levels of psychological distress, 60 eligible participants will be invited to partake in the study. Participants will be assigned a case number, to protect their identity and provide anonymity. Participants will be asked to provide written consent in Dutch/English and/or Dari and be made aware that they are permitted to withdraw from the study at any point.

#### 2.2.2 Sample Size

Since this is a pilot RCT no power calculations have been carried out. The total sample size will be 60 persons, with half of the participants receiving PM+ EP (N=30) and half assigned to the waiting group (n=30). Randomization will be carried out using a random numbers table generated by computerised software. Those participants in the waiting group will be offered the chance to receive the intervention

post-study. The total number included in the study allows us to evaluate the feasibility and acceptability of the intervention and allow for drop-out rates and incomplete data to be omitted. For the Process Evaluation, a non-random sample size of ten people will be interviewed.

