## Abstract

**Background:** A large portion of Afghanistan's population, particularly children, has endured prolonged conflict, poverty, and displacement, leading to significant psychological distress. As children grow into adolescence and adulthood, this distress often manifests in mental health symptoms and an increased likelihood of violent behaviours. With limited mental health professionals and strong stigma around mental health in Afghanistan, culturally adapted, evidence-based interventions are needed.

**Objective:** The study aims to explore the feasibility and acceptability of culturally adapted mental health intervention Problem Management Plus with an additional Emotional Processing module (PM+ EP), in reducing psychological distress in young Afghans. The primary objective is to assess the feasibility of delivering this intervention in Afghanistan and its acceptability by the target communities, and the secondary objective is to assess symptom reduction and behavioural change.

**Methods:** This is a pilot Randomized Control Trial (RCT) with participants aged 16 to 30 in Afghanistan. Eligible participants, young Afghans with high levels of distress and impaired functioning - measured by the Kessler Psychological Distress Scale (K10) -, will be randomized to PM+ EP (n=30) or the waiting group (n=30). The participants will be evaluated through self-report questionnaires at three time points; baseline (T1), four weeks later immediately post-intervention (T2), and 3 months post-intervention (T3), and through a qualitative interview (Process Evaluation) at the end of the study. Outcomes will include measures of anxiety and depression (HSCL-25), aggressive behaviours (AGQ), PTSD symptoms (PCL-5), and daily functioning (WHODAS 2.0).

**Results and Conclusion:** This study will assess the feasibility and acceptability of culturally adapted PM+ EP in Afghanistan and explore the relationship between mental health symptoms and violence among young Afghans. It will be the first to evaluate the feasibility of PM+ EP with this population and could pave the way for a large define RCT examining the effectiveness this approach, should the results show promise.

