## 2.5.2 Feasibility Measures

The primary outcome of this study is to assess the feasibility and acceptability of PM+ EP among young populations in Afghanistan. Feasibility will be evaluated based on participant retention rates, intervention and assessment completion rates, and the frequency of engagement with provided resources. Acceptability will be assessed through participant feedback and dropout rates. Additionally, qualitative data from process evaluation interviews will provide further insights into feasibility and acceptability by exploring participants' perceptions of the intervention and their willingness to engage in future studies.

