### **3. Analysis**

To evaluate the feasibility and acceptability of the intervention, qualitative analysis will be conducted through interviews with participants and facilitators, in addition, quantitative data will be gathered on mental health symptoms and behavioral outcomes. Qualitative data will be analyzed using ATLAS.ti to explore participant experiences and inform future intervention development. Interview transcripts will be imported into the software for systematic coding. An initial coding framework will be developed both deductively, based on study objectives, and inductively, based on emerging data. Two researchers will independently code a subset of transcripts, refining the codebook through consensus discussions to ensure consistency. All transcripts will then be fully coded, and thematic analysis will be conducted to identify key patterns and relationships. Findings will be used to complement

---

 DSM-5 (PCL-5) in Persian, [Psychometric Properties of the Persian Version of the Posttraumatic Stress Disorder Checklist for DSM-5 \(PCL-5\)](#)

 [WCG Clinical Services: Improving Clinical Trial Quality & Efficiency](#)

quantitative outcomes, providing a deeper understanding of feasibility, acceptability, and potential mechanisms of change within the intervention. To analyse quantitative data, mean differences in subscale scores and total scores between baseline (T1) and follow-up assessments (T2 and T3) will be determined. Linear mixed models will be employed to analyze feasibility and acceptability data, with treatment as a fixed effect, baseline endpoint measurements as covariates, and subjects as a random effect. This approach will allow for the assessment of trends in participant retention, session attendance, and intervention adherence over time while accounting for individual variability.

Feasibility will be assessed through intervention-specific metrics, including recruitment and consent rates, session attendance, assessment completion, protocol adherence, and occurrences of adverse events. Qualitative data collected through Process Evaluation interviews will complement these findings, providing contextual insights and a deeper understanding of the feasibility and acceptability of the program.

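### Section 3 assigns the baseline-adjusted mixed model to retention and attendance data, which it does not fit, and leaves the T1–T3 questionnaire scores with mean changes only

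*Protocol*

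**What the plan says.** Section 3 (Analysis) deals with the quantitative data in three consecutive sentences. For the questionnaires, "mean differences in subscale scores and total scores between baseline (T1) and follow-up assessments (T2 and T3) will be determined". No model and no contrast between arms is named for them. Then comes the model: "Linear mixed models will be employed to analyze feasibility and acceptability data". Its terms are specified in the same sentence as "with treatment as a fixed effect, baseline endpoint measurements as covariates, and subjects as a random effect". The sentence after that gives the purpose of the model as following retention, attendance and adherence over time.

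The questionnaires are the HSCL-25, AGQ, PCL-5 and WHODAS 2.0, completed by all participants at T1, T2 and T3 (Section 2.3 and Table 1). They serve the secondary objective; the Abstract states that "the secondary objective is to assess symptom reduction and behavioural change". Section 2.5.2 already frames the primary measures as proportions: "Feasibility will be evaluated based on participant retention rates, intervention and assessment completion rates".

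Section 2.2.2 sets 30 participants per arm without a power calculation. Its justification reads "The total number included in the study allows us to evaluate the feasibility and acceptability of the intervention", followed by "allow for drop-out rates and incomplete data to be omitted".

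**The concern.** The model and the data do not match. A baseline covariate and a random subject effect need an outcome measured before treatment and again afterwards. The questionnaires have this structure; retention, attendance and adherence do not. As written, the analysis of the feasibility data cannot sensibly be carried out, and the scores are left with the weaker analysis. A statistical analysis plan that followed the protocol would inherit both problems.

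At stake is the quality of the secondary symptom and behaviour estimates: some precision in any case, and some protection against selective drop-out if the drop-out is related to scores already observed. The primary feasibility rates can be computed without any model.

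**Working it through.** **Figures in the plan.** 30 + 30 = 60 agrees. There is no power, SD, correlation or drop-out figure to reproduce, so everything below beyond the 30 per arm is assumed.

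**1. Does the model fit the data it names?**

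| Data | Baseline value | Waiting-group comparator |
|---|---|---|
| Retention | None: everyone randomised starts as retained | Yes |
| Session attendance, adherence | None | None: the waiting group is offered PM+ EP only after the study |
| HSCL-25, AGQ, PCL-5, WHODAS 2.0 | T1 score | Yes, at T2 and T3 |

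Only the last row supplies what the model requires.

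**2. Precision.** Assumed: SD 1, equal correlation ρ between visits, random drop-out of 20% or 30% in both arms, so n = 24 or 21 per arm at T3.

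- Complete-case change: SE = √[2(1−ρ) · 2/n]. For ρ = 0.5, 0.6, 0.7 this is 0.289, 0.258, 0.224 (n = 24) and 0.309, 0.276, 0.239 (n = 21).
- Baseline-adjusted: SE = √[(1−ρ²) · 2/n]. The ratio to the line above is √[(1+ρ)/2] = 0.866, 0.894, 0.922, a reduction of 13%, 11%, 8% from baseline adjustment alone.

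Simulation with 30 per arm and 4,000 replicates gave these standard errors for ρ = 0.5 / 0.6 / 0.7:

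| Drop-out | Complete-case change | Complete-case ANCOVA | Mixed model |
|---|---|---|---|
| 20% | 0.290 / 0.257 / 0.226 | 0.254 / 0.232 / 0.210 | 0.251 / 0.228 / 0.206 |
| 30% | 0.312 / 0.272 / 0.240 | 0.277 / 0.247 / 0.225 | 0.273 / 0.242 / 0.218 |

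Mixed model against change: from 1 − 0.251/0.290 = 13% to 1 − 0.206/0.226 = 9%. The ANCOVA column shows that most of the gain is baseline adjustment.

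**3. Bias under selective drop-out.** Assumed: no true effect, and a proportion p lost before T3 in PM+ EP only, all from the worse half of the named score. Negative values favour PM+ EP.

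For drop-out by T1–T2 change, that change has SD √[2(1−ρ)], and the slope of T1–T3 change on it is (1−ρ)/[2(1−ρ)] = 0.5. The bias of complete-case change is therefore −0.5 · √(2/π) · p/(1−p) · √[2(1−ρ)].

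- p = 0.2: −0.100 (ρ = 0.5) to −0.077 (ρ = 0.7).
- p = 0.3: −0.171 to −0.132.
- Against SE = √[2(1−ρ)(1/n + 1/30)] with ρ = 0.5: 0.100/0.274 = 0.36 (n = 24) and 0.171/0.285 = 0.60 (n = 21) of a standard error.

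Simulated ranges over ρ = 0.5–0.7 and p = 20–30% (1,000,000 per arm):

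| Drop-out depends on | Complete-case change | Mixed model |
|---|---|---|
| T1–T2 change | −0.08 to −0.17 | 0.00 |
| T1 score | +0.06 to +0.17 | 0.00 |
| T2 score | 0.00 | 0.00 |
| Unseen T3 score | −0.06 to −0.17 | −0.09 to −0.23 |
| Unseen T1–T3 change | −0.15 to −0.34 | −0.11 to −0.23 |
| Nothing (random) | 0.00 | 0.00 |

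A gentler assumption (logistic dependence on T1 score or T1–T2 change in one arm, random loss in the other, ρ = 0.5 or 0.7, true difference −0.5 SD) gave an absolute complete-case bias of 0.05–0.09 SD at 20% and 0.08–0.13 SD at 30%. An estimate using all T1 and T2 data recovered −0.50. Together the two sets give the 0.05–0.17 SD range for drop-out that depends on observed scores. When both arms followed the same mechanism, the between-arm bias was zero in the cases tested.

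**The case against.** **The label may simply be loose.** Section 3 opens by mentioning symptom and behavioural data together with the evaluation of feasibility, the mixed-model sentence directly follows the one on scores, and a baseline endpoint makes sense only for questionnaires. The authors may have meant the scores. That is plausible as intent, but the next sentence names retention, attendance and adherence as the target. The text needs correcting on either reading.

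**The bias figures are assumptions.** The protocol gives no drop-out rate or mechanism, and the harsher scenario removes 60% of the worse half of one arm at 30% drop-out. Nor does Section 3 say that mean differences are compared between arms; I assume such a contrast because the trial is randomised. This stands, so the bias is conditional and secondary to the mismatch.

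**The mixed model is not a cure.** Under drop-out by unseen T3 score its bias is 34–45% larger than that of complete-case change (0.133 against 0.099; 0.148 against 0.102). This also stands.

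**Stronger readings that the documents do not support.**

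- A reader might take Section 2.2.2 as a complete-case rule, or infer that drop-outs leave the retention and completion denominators. The phrase is part of a sample-size justification and names no score, visit or analysis set; it most likely means that 60 leaves room for losses. A missing-data rule may properly sit in a statistical analysis plan.
- A reader might infer that a biased symptom difference would decide whether a larger trial follows. The Abstract says the study "could pave the way for a large define RCT examining the effectiveness this approach, should the results show promise", but that closes a sentence about evaluating feasibility, and Section 5 ties further implementation to feasibility and acceptability. No section makes the symptom difference a progression criterion.

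**Conclusion.** The mismatch in Section 3 is real and rests on the text alone. The planned model does not suit the feasibility measures, while the questionnaire scores that do suit it are given only changes from baseline.

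The dependable benefit of correcting this is modest precision, subject to the assumed correlations and random loss. Protection against bias is a further benefit only where drop-out depends on observed scores and differs by arm. The Section 2.2.2 phrase is a wording matter, not evidence of a faulty missing-data rule. Severity is minor, because the estimates concerned are secondary and the pilot was not powered for them.

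**What to change.** **Section 3.**

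- Apply the baseline-adjusted linear mixed model to the T2 and T3 scores of the four questionnaires, comparing the arms as randomised and using every observed value. How visit enters the model can be left to the statistical analysis plan.
- Report retention, assessment completion and dropout as rates among all randomised participants, and session attendance as a rate among those assigned to PM+ EP.
- Say that the model guards against drop-out related to observed scores, not against drop-out related to unseen ones. A complete-case result alongside would show how much the choice matters.

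**Section 2.2.2.** Replace the reference to omitting data with a statement that 60 participants allow for drop-out, so that it cannot be read as a complete-case rule.

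**Cost.** A few sentences and slightly more analysis work; no new data and no more participants.

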### 2.3 Procedure

Participants receiving PM+ EP will meet their facilitator individually, someone of the same gender, and receive the intervention through sessions conducted over Zoom or a similar platform; mitigating the difficulties around accessing psychological support, and the risks associated with safety of participants and stigma around mental health. Participants will receive six individual sessions of PM+ EP over the period of one calendar month.

All participants will complete four surveys for assessment at study points T1, T2 and T3; The Hopkins Symptom Checklist 25 (HSCL-25) to measure for anxiety and depression (Mollica et al, 1987), The Aggression Questionnaire (AQG) to measure violent behaviours (Buss and Perry, 1992), The Post Traumatic Stress Disorder (PTSD) Checklist for DSM-5 (PCL-5) will screen participants for symptoms of PTSD (Weathers et al, 2013), and cognitive ability and overall ability to function will be measured by WHO Disability Assessment Schedule 2.0 (WHODAS 2.0) (WHO, 2012). The latter has been used in studies looking at PTSD and other trauma-symptoms in low-resource settings, to assess the communities' impaired daily functioning (Hamdani et al., 2020). After the final assessment has been complete, a non-random sample of participants will be invited to partake in an interview – the Process Evaluation -, to gather qualitative data to assess the feasibility and acceptability of the program.

The timeline and frequency at which the instruments that will be used for screening, baseline and post intervention are listed in the table below. Some of the listed instruments have translations in Dari or Farsi (Afghan Persian/Iranian Persian). In case there is no translation, the instrument will be translated and back translated by the research team.

*Table 1. Measure Overview and Timeline*

Assessment Timeline					
Enrolment T0	Allocation	Baseline T1	Post-intervention T2	Follow-up - 3 months Post- intervention T3	Close-out
Enrolment:					
Eligibility criteria	X				
Informed consent	X				
Allocation		X			
Intervention:					
PM+ EP		X	X	X	X
Waiting Group					
Assessment:					
K10	X				
HSCL-25		X	X	X	
AGQ		X	X	X	
DSM-5 (PCL-5)		X	X	X	
WHODAS 2.0		X	X	X	
Process Evaluation					X

#### 2.3.1 Facilitators

The PM+ EP intervention will be delivered by facilitators who are Afghan and speak the Dari language. Future adaptations may allow for a wider variety of Afghan languages. Facilitators will be trained to

deliver the PM+ EP program sessions to participants, by a PM+ Training expert, in addition to carrying out consent and screening procedures. The facilitators will be recruited based on their qualifications and experience and receive a three-day training on delivering the culturally adapted PM+ EP, psychological first aid (PFA), selfcare techniques, and ethics in research. Following training, facilitators will be required to role play practice cases using case studies provided by the research team and will receive bi-weekly supervision throughout the program by a PM+ supervisor, alternating between group supervision and individual supervision; allowing facilitators to learn from peers and from their supervisor. Facilitators must be fluent in Dari and preferably have a good knowledge of English.

### 2.3.2 Process Evaluation

After the study, participants will be approached for the Process Evaluation; sampling five people ensuring variance on gender, age, and completion of the program (drop out/completed), to partake in a qualitative interview. Five mental health providers who delivered the intervention PM+ EP will also be approached to participate in the qualitative interviews. The objective of this process is to understand the perspectives of those who received the intervention and those who delivered the intervention, on the feasibility and acceptability of the program among their own communities and in their country, and the perceived change in mental health symptom and behavioural change for themselves or the participants. This will provide insight into the possibility of scaling the study and providing the intervention on a wider scale. The Process Evaluation will use a semi-structured interview script to collect qualitative data, and participants will be asked about their experiences with the intervention, ease of adherence to the intervention, thoughts on the recruitment process, the PM+ EP facilitators and their approach, and whether the program could be effectively integrated into health systems in Afghanistan.

### 2.3.3 Outcomes

In this pilot RCT, the primary outcome is to explore the feasibility and acceptability of delivering the PM+ EP intervention in Afghanistan. The study serves to demonstrate whether such interventions could be safely scaled and produce positive outcomes for the target population. The study's secondary outcome is to analyse the relationship between mental health and violence, and to discuss the potential for impact of culturally adapted mental health programming on symptom-change and behavioral change, in particular in reducing violence, and to illustrate the context-specific linkages between mental health and violence. Through this research, we can examine the mental health symptoms, risk factors, and functional impairment, caused by ongoing exposure to conflict or adversity, and advocate for scaling-up adaptation and implementation of evidence-informed mental health interventions in countries such as Afghanistan.

## 2.4 Intervention: Program Management Plus (PM+) with Emotional Processing (EP) Module

PM+ EP comprises of Problem Management Plus, an evidence-based low intensity psychological intervention developed by the World Health Organization (WHO), with an additional Emotional Processing module specifically to address psychological distress related to trauma exposure. The core of the intervention is designed for adults impaired by distress in communities exposed to conflict and adversity; it consists of CBT techniques that have been adapted for communities that do not have good availability of specialist care. The additional module was developed by researchers treating

refugee youth (Alozkan Sever et al, 2021). For this study, PM+ EP will be a six-session individual and guided support program. The original sections of PM+ are available in many languages including Farsi, and the additional EP module will be translated by PoMA's Afghan translator. The sessions cover the topics of managing stress, strengthening social support, staying well and persevering. PM+ includes the strategies problem solving, stress management, behavioural activation and accessing social supports. The additional EP module aims to address negative emotions related to memories of adverse and potentially traumatic events, which are common amongst much of the population in Afghanistan and so particularly relevant to recovery and healing. The module consists of guiding participants to recall and explore both adverse and positive autobiographical memories—conceptualized as 'puzzle pieces'—which they symbolically assemble like a jigsaw to facilitate emotional integration; the module concludes with a positive imagery exercise where participants envision an ideal future, fostering resilience and goal-oriented thinking. PM+ EP works not only to treat the symptom in the immediate, but to help build resilience in participants and help them feel prepared for any future traumatic events. The intervention provides adaptive skills to participants that help them improve or cope with the mental health symptoms they experience.

Initially, our research team will engage with the target population and conduct in-depth qualitative interviews with a variety of persons through key-informant interviews (KIIs). These will cover a broad range of questions related to cultural perceptions towards mental health, violence, and the relationship between the two. The team seeks to gather information on the target population's mental health needs, where they seek help, and how cultural context and stigma around mental health impacts them; to inform on the adaptation process of the PM+ EP intervention. Cultural adaptation of PM+ EP should consider adapting the intervention's language, visuals, cultural concepts of mental health, treatment goals, and incorporating culturally sensitive and de-stigmatizing delivery methods, in such a way, that it is compatible with the client's "cultural patterns, meanings, and values" (Bernal and Rodriguez, 2009). Heim's new framework for cultural adaptation focuses on three main possible aspects for adaptation; cultural concepts of distress, treatment components, and treatment delivery (Heim and Kohrt, 2019). Following adaptation of PM+ EP, facilitators will be trained to provide the intervention, and a pilot randomized control trial (RCT) will test the adapted PM+ EP with this population.

